7.4 Demographic and Other Baseline Characteristics

All demographics and baseline characteristics will be summarized by safety analysis set in Part 1 escalation cohorts and Part 2 expansion cohorts and by full analysis set in Part 3 extension cohorts.

Demographics

Demographic data to be evaluated will include age, sex, race, ethnicity, height, and weight.

Stratification factors (Part 3 only)

- Type of Myeloma
 - IgA
 - Other
- Cytogenetic
 - High risk [(del17, t(4;14) and/or t(14;16)]
 - Standard risk

Disease characteristics:

- Years since initial diagnosis [(date of first dose – date of diagnosis) / 365.25)].
- Type of Myeloma
 - IgG, IgA, IgD, IgM, Biclonal (if known, otherwise summarize with Light chain below).

- Light Chain Kappa, Light Chain Lambda, Light chain Biclonal, Light Chain unknown.
- Measurable disease
 - Measurable by both SPEP (baseline serum M-protein ≥ 0.5 g/dL) and UPEP (baseline urine M-protein ≥ 200 mg/24 hr)
 - Measurable by SPEP only
 - Measurable by UPEP only
 - Measurable by FLC only (met all three criteria below):
 1. Involved either Kappa or Lambda free light chain level at baseline ≥ 10 mg/dL;
 2. and FLC ratio (Kappa FLC/Lambda FLC) is abnormal (serum FLC ratio > 1.65 or < 0.26)
 3. and not measurable by SPEP or UPEP
 - Non-measurable (not measurable by SPEP, UPEP, or FLC)
- Durie-Salmon Stage.
- International Staging System (ISS) at initial diagnosis.
- International Staging System (ISS) at study entry.
- Evidence of Lytic Bone Disease at initial diagnosis.
- Evidence of Extramedullary Disease at initial diagnosis.
- Eastern Cooperative Oncology Group (ECOG) performance status.

Baseline disease characteristics—laboratory values

- β_2 -microglobulin category (< 2.5 , $2.5-5.5$, > 5.5 mg/L).
- Serum albumin category (< 3.5 , ≥ 3.5 mg/dL).
- Serum creatinine category (≤ 2 , > 2 mg/dL).
- Calculated creatinine clearance category (< 30 , $30 - < 60$, $60 - < 90$, ≥ 90 mL/min).
Creatinine clearance will be calculated using the Cockcroft-Gault formulas as follows:

For male patients:

$$\text{creatinine clearance} = \frac{(140 - \text{Age[yrs]}) \times \text{weight[kg]}}{72 \times (\text{serum creatinine [mg/dL]})}$$

For female patients multiply by 0.85.

- Hemoglobin (g/L).
- Platelet count (10^9 /L).
- Absolute neutrophil count (10^9 /L).
- Lactate dehydrogenase (LDH) $>$ Upper limit of normal (ULN).

Baseline Bone Marrow Evaluation

- Baseline bone marrow aspirate/biopsy performed and adequate for interpretation.

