3. If the PD is due to imaging (plasmacytomas or bone lesion), the PD can be considered as a confirmed PD.

4. If only one PD is recorded as the last available assessment before the patient discontinues the treatment due to PD, it can be counted as a confirmed PD.

Best M-Protein Response

The best m-protein response is defined as the percent change from baseline to the best (lowest) value post-baseline. For subjects with both measurable serum and urine m-protein at baseline, the best m-protein will be the worse (i.e. lower percent reduction) of the best serum m-protein and the best urine m-protein. For subjects with only measurable serum m-protein at baseline, the

CONFIDENTIAL

best m-protein response is based on serum m-protein. For subjects with non-measurable serum m-protein at baseline, but measurable urine m-protein at baseline, the best m-protein response is based on the urine m-protein. If not measurable by serum or urine m-protein the best m-protein response is based on the difference between involved and unininvolved FLC. A waterfall plot of the best m-protein response will be generated. The plot will have the following information:

1. Response.
2. Dose.
3. Schedule.
4. Measurable categories: Both Serum and Urine M-protein/Serum M-protein/Urine M-protein/FLC.

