The maximum percent reduction will be plotted in the following hierarchical order:

- [1] Plot the worse (higher) value of the maximum percent reduction from baseline in serum and urine M-protein if the patient has both serum and urine M-protein measurable;
- [2] Plot Serum M-protein maximum percent reduction from baseline if data is available;
- [3] If [2] is not feasible, plot Urine M-protein maximum percent reduction from baseline if data is available;
- [4] If both [2] and [3] are not feasible, plot maximum percent reduction from baseline for difference between two types of Serum FLC if data is available.

Difference between two types of serum free light chain (FLC)

The percent change from baseline for difference between two types of serum FLC is defined as:

$$(\text{post-baseline difference} - \text{baseline difference}) / \text{baseline difference} * 100\%$$

To calculate the difference, the “involved” and “non-involved” light chains must be determined at first based on the ratio of non-missing values for Serum Kappa LC protein and Serum Lambda LC protein at baseline.

The detailed algorithm is provided as below:

- If the baseline ratio of (Kappa LC/Lambda LC) > 1.65 , then Kappa LC is defined as involved FLC, and Lambda LC is defined as non-involved FLC. Then:
Difference between involved and uninvolved = Kappa LC-Lambda LC
- If the baseline ratio of (Kappa LC/Lambda LC) < 0.26 , then Lambda LC is defined as involved FLC, and Kappa LC is defined as non-involved FLC:
Difference between involved and uninvolved = Lambda LC-Kappa LC
- If the baseline ratio of (Kappa LC/Lambda LC) ≤ 1.65 and ≥ 0.26 , then “involved” and “non-involved” FLC cannot be determined (ratio is normal), and maximum percent reduction from baseline for difference between two types of Serum FLC won’t be available.

7.8.2.2 *Secondary Efficacy Analysis*

ORR based on Investigator Assessment

ORR based on investigator-assessed response will be analyzed as one of the secondary endpoints. It will be analyzed based on the confirmed responses by using the same analysis approach as for IRC-assessed ORR.

DOOR

DOOR is defined as the time from first documented evidence of confirmed PR or better until the earliest date of a confirmed PD per IMWG, or death among patients who achieve a response (i.e., confirmed PR or better). Responders without confirmed PD or death will be censored at the censoring time point for PFS as specified in Table 1.

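### The Part 3 waterfall plot chooses its marker by whether data are available, not by whether the marker was measurable at baseline, so some urine-only and light-chain-only patients can be plotted on the wrong marker

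*SAP*

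**What the plan says.** SAP 7.8.2.1 asks for a waterfall plot of each Part 3 patient's maximum percent reduction, by dose level and colour-coded by marker, using a four-step order:

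- Step [1] takes the worse of serum and urine "if the patient has both serum and urine M-protein measurable".
- Step [2]: "Plot Serum M-protein maximum percent reduction from baseline if data is available".
- Step [3]: "If [2] is not feasible, plot Urine M-protein maximum percent reduction from baseline if data is available".
- Step [4]: "If both [2] and [3] are not feasible, plot maximum percent reduction from baseline for difference between two types of Serum FLC", again subject to data being available.

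Only step [1] tests measurability.

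SAP 7.8.1 (Best M-Protein Response) sets the rule for the Part 1 and 2 waterfall plot. Serum is used where serum is the only measurable M-protein. Urine is used "For subjects with non-measurable serum m-protein at baseline, but measurable urine m-protein at baseline". The last branch is "If not measurable by serum or urine m-protein the best m-protein response is based on the difference between involved" and uninvolved light chains. Every branch turns on measurability at baseline.

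SAP 7.4 sets the limits at 0.5 g/dL for serum and 200 mg/24 h for urine. It tabulates urine-only and FLC-only patients as separate categories, the latter being "and not measurable by SPEP or UPEP". Protocol 7.1, inclusion criterion 3, admits Part 3 patients on any one of the three markers.

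**The concern.** In Part 3, serum and urine M-protein are measured centrally at screening and in each treatment cycle for all patients (Protocol 9.3.10.4 and Appendix A Tables 12 and 13). Serum data will therefore normally exist even where serum does not measure the patient's disease. Because step [1] says measurable and steps [2] to [4] do not, a programmer would reasonably read the later steps as a different and weaker condition.

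The bar for such a patient would then show the percent change of a small sub-threshold value. It could disagree with the patient's response category, because Protocol Appendix F bases partial response on FLC when serum and urine are not measurable. The plot would also follow a different rule from its Part 1 and 2 counterpart.

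The protocol names one plausible source of small serum values. Part 3 patients are refractory to an anti-CD38 antibody, no washout from daratumumab or isatuximab is required (Protocol 7.2, criterion 4), and a recently given antibody can make serum electrophoresis positive (Protocol 9.3.10.7). Clearance of that antibody could look like a deep reduction.

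What is at stake is the accuracy of a descriptive figure shown by dose level.

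**Working it through.** The plan states no figure here, so there is none to reproduce. The check applies the two selection rules to the same patients. **All patient values are assumptions**, chosen to show how the rules behave.

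Inputs: measurability limits of 0.5 g/dL (serum) and 200 mg/24 h (urine), from SAP 7.4; the step order in SAP 7.8.2.1; the measurability rule in SAP 7.8.1.

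Formula: percent change = (post - baseline) / baseline × 100. With a baseline of 0 it cannot be computed; the step is then treated as not feasible and the next one applies.

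| Assumed patient | SAP 7.8.2.1 as written | SAP 7.8.1 rule |
|---|---|---|
| Urine-only: serum 0.3 to 0.1, urine 1200 to 1100 | serum: (0.1 - 0.3)/0.3 = -66.7% | urine: (1100 - 1200)/1200 = -8.3% |
| Urine-only: serum 0.2 to 0.2, urine 1200 to 60 | serum: 0% | urine: (60 - 1200)/1200 = -95% |
| FLC-only: serum 0.2 to 0, FLC difference 60 to 57 | serum: (0 - 0.2)/0.2 = -100% | FLC: (57 - 60)/60 = -5% |
| FLC-only: serum 0, urine 50 to 25, FLC difference 60 to 57 | urine: (25 - 50)/50 = -50% | FLC: -5% |
| Urine-only: serum 0, urine 1200 to 1100 | urine: -8.3% | urine: -8.3% |
| FLC-only: serum 0, urine 0, FLC difference 60 to 20 | FLC: (20 - 60)/60 = -66.7% | FLC: -66.7% |
| Serum-only: serum 2 to 0.8 | serum: (0.8 - 2)/2 = -60% | serum: -60% |
| Both measurable: serum 2 to 0.8, urine 1000 to 900 | worse of -60% and -10% = -10% | -10% |

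Units: serum g/dL, urine mg/24 h, FLC difference mg/dL.

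The first four rows differ, and in both directions: three overstate the reduction and one hides it. The last four agree. The rules therefore part only for:

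1. a urine-only or FLC-only patient with a quantifiable serum value below 0.5 g/dL; and
2. an FLC-only patient with no computable serum change and a quantifiable urine value below 200 mg/24 h.

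**The case against.** Several points on the other side stand.

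- **Scope.** A reader might infer that step [2] captures every patient not caught by step [1], so that all urine-only and FLC-only patients are misplotted. It does not: a baseline of 0 makes the step infeasible, and the order moves on. A urine-only patient then reaches urine; an FLC-only patient reaches FLC if urine is also 0.
- **Number.** A reader might assume that 10% to 30% of patients are urine-only or FLC-only and conclude that 12 to 35 of 118 bars per arm are wrong (0.10 × 118 = 11.8; 0.30 × 118 = 35.4). The documents give no such share. Even on that assumption these are upper bounds, reached only if every such patient has a quantifiable sub-threshold value.
- **Whether such patients can enter.** Footnote n to the Part 3 serum M-protein row (Protocol Appendix A Table 12) requires a screening level of at least 500 mg/dL. Read literally, every Part 3 patient would have measurable serum and the problem would vanish. That reading conflicts with inclusion criterion 3, and the SAP 7.4 categories allow for such patients. It is a conflict to resolve, not an answer.
- **Meaning of available.** SAP 7.8.2.1 treats the FLC reduction as unavailable when the baseline ratio is normal, even though both chains were assayed. Available may thus mean more than assayed. But nothing there supplies a measurability limit for serum or urine.
- **Consequence.** A reader might infer that the efficacy result is at risk. It is not. The plot feeds no endpoint, and the colour-coding shows which marker each bar uses. It does not show whether that marker was measurable.

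**Conclusion.** The concern holds as a specification defect in one descriptive figure. As written, steps [2] to [4] can plot a urine-only or FLC-only patient on a marker that does not measure the disease, with an error that can be large and can go either way. It affects only patients with a quantifiable sub-threshold serum value, or, for FLC-only patients without a computable serum change, a quantifiable sub-threshold urine value. Their number cannot be derived from the documents.

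This rests on two assumptions: that inclusion criterion 3 governs over footnote n, and that a zero baseline counts as not feasible.

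IRC-assessed ORR and its exact interval, the futility boundaries (SAP 7.13) and the success criterion of 33 responders among 118 (SAP Appendix D) are unaffected. The change is worth making because it is cheap and because the SAP already has the better rule.

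**What to change.** Restate steps [2] to [4] in SAP 7.8.2.1:

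- [2] serum M-protein, if measurable at baseline (≥0.5 g/dL);
- [3] otherwise urine M-protein, if measurable at baseline (≥200 mg/24 h);
- [4] otherwise the involved-minus-uninvolved FLC difference, if it can be computed.

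This matches SAP 7.8.1. Step [4] should not import the FLC threshold from SAP 7.4: SAP 7.8.1 has none, and adding it could drop bars from a plot meant to show each patient.

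In the same edit:

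- Reconcile the direction of worse. Step [1] calls it the higher value of the maximum percent reduction; SAP 7.8.1 calls it the lower percent reduction. The two agree only if step [1] means a signed change, so the sign convention should be stated.
- Reconcile footnote n of Protocol Appendix A Table 12 with inclusion criterion 3.

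The cost is a few words in the SAP and a small programming change, since the measurability categories are already derived under SAP 7.4. A patient measurable on neither M-protein and with a normal baseline FLC ratio would have no bar. Inclusion criterion 3 should exclude such a patient; any who appear can be listed in a footnote to the figure. The footnote n correction needs a protocol clarification.

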7.8.2.3 Exploratory Efficacy Analysis

MRD negativity at a sensitivity of 10^{-6}

MRD negativity at a sensitivity of 10^{-6} as an exploratory endpoint is defined as patients who are MRD negative at a sensitivity of 10^{-6} in patients achieving suspected CR. Duration of MRD negativity (10^{-6}) is defined as the time from the first MRD negative status (10^{-6}) to the earliest date of the MRD positive status (10^{-6}), confirmed PD per IMWG or death.

For MRD negativity (10^{-6}) rate based on bone marrow testing, the number and percentage of patients who have achieved MRD negativity (10^{-6}) will be summarized by dose level. The corresponding exact 95% CI for MRD negativity (10^{-6}) rate will also be provided. The rate of maintaining MRD negativity (10^{-6}) will be reported in patients who achieve CR and MRD negativity (10^{-6}). Duration of MRD negativity (10^{-6}) will be analyzed using the Kaplan-Meier method in patients who have achieved MRD negativity (10^{-6}) when data permit; otherwise, a listing will be generated.

Time to Response (TTR)

Time to response is defined as the time from first dose to the date of first documentation of confirmed response (PR or better). Patients without confirmed response will not be included in the analysis of TTR.

Descriptive statistics including mean, median, standard deviation, minimum, maximum, Q1 and Q3 will be summarized in responders.

In addition, time to the best response will be analyzed by using the same approach in responders.

7.8.2.4 Subgroup Efficacy Analysis

For the primary endpoint ORR by IRC assessment, subgroup analysis will be performed in the following selected subgroups.

Subgroups	Categories
Age group (at screening)	e.g. 18 to <70 ; ≥ 70
Gender	Male; female

Race	White; Black; Asian; Other
Type of myeloma	IgA; IgG; light chain only
Cytogenetics risk	High risk [defined as 17p-, t(4;14) and/or t(14;16)]; complementary standard risk (non-high risk) Expanded high risk [defined as High risk and/or 1q21 amplification/gain]; complementary standard risk (non-expanded high risk)
Prior treatment	Anti-CD38 in last line of therapy; IMiD in last line of therapy; Recently approved agents (Selinexor, Anti-BCMA CAR-T, belantamab); Bispecific T-cell engagers; Anti-BCMA exposed; Anti-BCMA exposed (CAR-T); Anti-BCMA exposed (ADC); Anti-BCMA exposed (Bispecific T-cell engagers); Penta exposed.
Number of prior lines of therapy	≤4, >4
Refractory to prior anti-cancer therapy	Anti-CD38 monoclonal antibody; CAR-T; IMiD (Lenalidomide, Pomalidomide, Thalidomide); Proteasome Inhibitor; Triple refractory (IMiD, PI, and anti-CD38); Penta refractory (Bortezomib, Carfilzomib, Lenalidomide, Pomalidomide and anti-CD38); Anti-BCMA refractory; Triple refractory and bispecific T-cell engager exposed.

In the subgroup analysis, ORR will be presented using forest plot within each treatment arm for the following categories: age, gender, race, type of myeloma, cytogenetic risk group, prior treatment, number of prior lines of therapy, and refractory to prior anti-cancer therapy. Other subgroups may be explored if data permits, but not required by this SAP. If the percentage of subjects is small within a particular subgroup, then the subgroup categories may be refined prior to the primary analysis of Part 3 extension.

7.9 Patient-Reported Outcomes (Part 3 only)

Patient-reported outcome measures will be analyzed using the PRO analysis set. The primary PRO score of interest will be the EORTC QLQ-MY20 disease symptoms subscale at approximately 12 weeks (C4D8). Data preparation steps will include those described in Appendix F. PRO analyses will only include observations that fall within “windows” specified in Appendix F.

EORTC QLQ-MY20

The actual value and nominal change from baseline of the EORTC QLQ-MY20 subscale scores will be summarized using descriptive statistics overall and by dose arm over time, with 95% CIs, and presented both in tables and figures.

Considering sufficient sample sizes and follow-up data for model convergence, mixed models for repeated measures (MMRM) may be conducted to examine the change from baseline in EORTC QLQ-MY20 single or multi-item subscales. The models will include the following covariates: treatment, visit, baseline score, and any variables that were used as randomization factors (cytogenetic risk, myeloma type). The models for all EORTC QLQ-MY20 subscales will be first conducted using unstructured covariance structure; if any subscale model does not converge, then compound symmetry or autoregressive (1) [AR(1)] covariance structures will be considered. The repeated measures analysis will use assessments collected per the schedule of events in the protocol (see Appendix F). The estimated least squares (LS) mean change in score from baseline with 95% CIs will be reported at each treatment cycle visit (time point) for each treatment arm. However, no comparison will be made between the treatment arms. LS mean changes from baseline with 95% CIs will be graphically presented over time.

In addition, there will be empirical cumulative distribution functions of change in scores from baseline at each visit per treatment group, to provide information to help support the interpretation of the results. Calculate the $P(X \leq x)$ for each EORTC QLQ-MY20 subscales, and plot as cumulative distribution functions (CDFs), characterized by an S-shape rising from 0% to 100% on the y-axis (i.e., lower to higher, from left to right). For EORTC QLQ-MY20 functional subscales, the arrow pointing to the left of zero ($X < 0$) is “Worsening,” and the arrow pointing to the right of zero ($X > 0$) is “Improvement”; for the EORTC QLQ-MY20 symptom subscales, the arrow pointing to the left of zero ($X < 0$) is “Improvement,” and the arrow pointing to the right of zero ($X > 0$) is “Worsening”. These CDF curves depict the cumulative probability on the y-axis that a patient will report a change from baseline on the EORTC QLQ-MY20 subscale less than or equal to the observed value “ x ” on the x-axis. The CDF curves will be provided for the visits if the number of patients per treatment arm is over 20.

The subscales of EORTC QLQ-MY20 are defined as shown in Table 3. Details of scoring and initial handling of missing data are included in the EORTC QLQ-MY20 scoring guidelines, which specifies that multi-item scales can be scored whenever at least half of the items in the subscale are completed: e.g., for the Disease Symptom subscale, at least 3 of items 1-6 will need to be completed. For EORTC QLQ-MY20, no imputations of missing PRO assessments will be performed.

Table 3 Subscales of EORTC QLQ-MY20

Subscale scores	Included items
Future perspective	18-20
Body image	17
Disease symptoms	1-6
Side effects of treatment	7-16

For each subscale score of EORTC QLQ-MY20, the number and percentage of patients with either a stable score, an improvement in score or a worsening in score from study entry based on a minimally important difference (MID) of 10 will be summarized by treatment arm from baseline to week 12 (C4D8). MID thresholds for functioning subscales: Improved = Change from baseline in subscale score ≥ 10 ; Stable = Change from baseline in subscale score ≤ 9 and ≥ -9 ; Worsening = Change from baseline in subscale score ≤ -10 . MID thresholds for symptom subscales: Improved = Change from baseline in subscale score ≤ -10 ; Stable = Change from baseline in subscale score ≥ -9 and ≤ 9 ; Worsening = Change from baseline in subscale score ≥ 10 .

Other MIDs and responder metrics may also be considered: e.g., Sully et al. (2019) defines the smallest difference in mean score between groups which could be considered clinically meaningful, as the minimally important difference (MID), while the threshold of within-patient change deemed meaningful, used to define a patient as a responder if their change in score exceeds this threshold, is referred to as the responder definition (RD); where EORTC QLQ-MY20 MID: Disease Symptoms (DS 10 points), Side Effects of Treatment (SE 10 points), Body Image (BI 13 points), and Future Perspective (FP 9 points); and, Responder definitions (RD): DS (16 improvement; 11 worsening), SE (6 improvement; 9 worsening), BI (33 improvement; 33 worsening), and FP (11 improvement; 11 worsening).

PRO completion over time and in overall will be calculated at the questionnaire level for the EORTC QLQ-MY20 in the full analysis set. Proportion of PRO score compliance will be

calculated as follows: (number of patients with the PRO score completed on Cycle X Day Y) / (number of patients for whom a PRO score is expected on Cycle X Day Y). A subject will be considered to have a PRO score “completed” on Cycle X Day Y if they have enough item scores to calculate at least one subscale score on the EORTC QLQ-MY20 questionnaire. A subject is “expected” to have a PRO score on Cycle X Day Y if treatment was received on Day 1 of the same cycle.

PRO ‘available data rate’ will also be calculated over time, and in overall at the questionnaire level for EORTC QLQ-MY20 in the full analysis set. Proportion of PRO score compliance will be calculated as follows: (number of patients with the PRO score completed on Cycle X Day Y) / the number of patients in the full analysis set i.e. number of patients consented and eligible to participate in the PRO data collection.

EQ-5D-5L

The EQ-5D-5L patient-reported questionnaire consists of 5 dimensions (5 items: mobility, self-care, usual activities, pain/discomfort, and anxiety/depression) each rated on 5 levels. The EQ-5D-5L also contains the Visual Analogue Scale (VAS); EQ VAS ranges from 0 (worst imaginable health state) to 100 (best imaginable health state).

EQ-5D-5L data will be analyzed using the PRO analysis set. Data preparation steps will include those described in Appendix F. EQ-5D-5L summaries and analyses will only include observations that fall within “windows” specified in Appendix F.

EQ-5D-5L (i.e., 5 individual item scores) will be analyzed by summarizing the raw item scores descriptively over time.

For EQ VAS, ranging from 0 to 100, the actual mean values and mean change from baseline, with 95% CIs, will be summarized using descriptive statistics in overall and by treatment group over time and presented both in tables and figures. As with EORTC QLQ-MY20, MMRM analyses may be considered, if sample sizes and follow-up data are sufficient.

PRO compliance over time and overall will be calculated at the questionnaire level for the EQ-5D-5L in the full analysis set. Proportion of PRO score completion and PRO ‘available data rate’ will be calculated following the approach for EORTC QLQ-MY20 above.

For EQ-5D-5L, no imputations of missing PRO assessments will be performed.

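### The optional PRO mixed model lists no treatment-by-visit term, so the per-arm LS mean curves it is meant to report at each visit are parallel by construction

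*SAP*

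**What the plan says.** SAP Section 7.9 makes the model conditional on sample size and follow-up: "mixed models for repeated measures (MMRM) may be conducted to examine the change from baseline" in the QLQ-MY20 subscales. If it is run, the mean structure is fixed by one sentence: "The models will include the following covariates: treatment, visit, baseline score, and any variables that were used as randomization factors", the last being cytogenetic risk and myeloma type. For the covariance, the models "will be first conducted using unstructured covariance structure", with compound symmetry or AR(1) as fallbacks.

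The output is visit-specific and arm-specific. The LS mean change and its 95% CI "will be reported at each treatment cycle visit (time point) for each treatment arm", and "LS mean changes from baseline with 95% CIs will be graphically presented over time". The SAP adds: "However, no comparison will be made between the treatment arms".

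The same section names the disease symptoms subscale at about 12 weeks, C4D8, as the main PRO score of interest. It also plans observed values and changes by arm over time with 95% CIs, empirical distribution functions of change by visit and arm, and counts of patients improved, stable or worse at C4D8 using a 10-point threshold.

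Nothing else supplies the missing term. Protocol Section 13.1.6 says only that linear mixed models may be explored and gives no fixed effects. The EQ VAS paragraph in SAP 7.9 points back to the QLQ-MY20 approach.

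**The concern.** The stated model cannot freely estimate the quantities it is asked to deliver. With treatment and visit as main effects only, the fitted gap between 120 mg and 240 mg is one number, used at every visit. Any divergence or convergence over cycles is averaged away, and the plotted curves will be parallel whatever the data show. The unstructured covariance does not help, because it governs within-patient correlation and leaves the mean profile constrained.

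C4D8 is the visit of most interest. Its LS mean in each arm would borrow the arm gap from C1D8, one week after the first dose, and from late cycles in which only selected patients remain. Part 3 is meant to identify the better dose from the totality of data, so a PRO figure that cannot show the doses separating over time is a poor contribution to that judgement.

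**Working it through.** **No figure to reproduce.** The documents give no sample size, power or expected profile for this model. The check is algebra, followed by two illustrations on assumed profiles.

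**Step 1: the constraint.** With the terms listed in SAP 7.9,

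LSmean(arm a, visit v) = μ + τ_a + π_v + (baseline and stratification terms at their reference values).

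The visit and covariate terms are common to both arms and cancel:

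LSmean(240, v) − LSmean(120, v) = τ_240 − τ_120, for every v.

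This holds under unstructured, compound symmetry or AR(1) covariance.

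**Step 2: size in a simple case.** Assumed, not from the documents: five balanced visits, 1:1 allocation, visits weighted equally, true change flat at 0 in arm A and 0, 2, 4, 6, 8 in arm B.

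- Fitted common gap: (0 + 2 + 4 + 6 + 8)/5 = 4.
- Mean of the two arms by visit: 0, 1, 2, 3, 4.
- Fitted arm A is that mean minus 2; fitted arm B is that mean plus 2.

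| Visit | True A | Fitted A | True B | Fitted B | Error per arm |
|---|---|---|---|---|---|
| 1 | 0 | −2 | 0 | 2 | 2 |
| 2 | 0 | −1 | 2 | 3 | 1 |
| 3 | 0 | 0 | 4 | 4 | 0 |
| 4 | 0 | 1 | 6 | 5 | 1 |
| 5 | 0 | 2 | 8 | 6 | 2 |

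SAP Appendix F gives the post-baseline QLQ-MY20 assessments as C1D8, C2D8, C3D8, C4D8 and so on, so C4D8 is the fourth. The error there is 1 point per arm, and the largest error at any visit is 2 points, against the 10-point threshold in SAP 7.9.

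**Step 3: check by simulation.** Assumed: six visits, SD 20, within-patient correlation 0.5, true gap 0, 2, 4, 6, 8, 10; generalised least squares with known covariance; 100 simulated trials of 118 per arm (the planned arm size), without dropout and with about 12% dropout per visit.

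| Model | Dropout | Mean estimated gap, visits 1 to 6 |
|---|---|---|
| Main effects | No | 4.94 at all six |
| Main effects | Yes | 3.23 at all six |
| With treatment-by-visit | No | −0.35, 2.11, 3.77, 5.90, 7.75, 10.19 |
| With treatment-by-visit | Yes | −0.18, 2.09, 4.18, 5.83, 7.95, 10.04 |

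The main-effects gap is constant, and its value depends on the dropout pattern. At the fourth visit with dropout the gap error is 6 − 3.23 = 2.77 points, or about 1.4 points per arm on an equal split. The interaction model recovers the assumed pattern.

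**The case against.** The best case for leaving the text alone is that little depends on this model. It is optional, no hypothesis or decision rule uses it, and the SAP rules out comparing the arms. The week 12 endpoint of no worsening is addressed directly by the responder categories at C4D8. The observed by-arm summaries and the distribution curves carry no parallel constraint. All of this stands, and it limits the importance of the point.

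It does not remove the point. The absence of a between-arm comparison does not protect the output, because each arm's own LS mean is what the constraint distorts. If the arms are not to be compared, there is less reason to tie their profiles together. The list of terms might not be exhaustive, and the programmed model could include the interaction, but nothing in the documents says so, and a programmer following the text would omit it.

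Two stronger readings are tempting. A reader might take the arm-gap error as the size of the problem: up to 4 points in the five-visit example. The gap is not a reported quantity; the per-arm error is half of it, and smaller again at C4D8. A reader might also infer that the week 12 PRO result is compromised. It is not, since the unmodelled summaries at that visit are planned separately.

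**Conclusion.** The point holds as a specification error in an optional, descriptive model. As written, the model forces parallel arm curves, and each arm's visit-specific LS mean is biased whenever the true profiles diverge. That part is algebraic and needs no assumption.

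The size does rest on assumptions, since the documents give no expected PRO profile. In the five-visit illustration it is at most 2 points per arm, and 1 point at C4D8, against a threshold of 10. A different divergence, dropout pattern or visit weighting would change those figures. If the true profiles are parallel, there is no bias from this source.

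**What to change.** In SAP 7.9, add treatment-by-visit to the listed fixed effects, or state that the model is fitted separately by arm. Apply the same to the EQ VAS model if it is run.

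Limit the modelled visits at the same time. Appendix F windows assessments to Cycle 48 or the maximum observed. With V visits modelled, the interaction adds V − 1 parameters: 4 for five visits, but 47 for the 48 Day 8 visits from C1D8 to C48D8, alongside an unstructured covariance. A workable cap is the rule SAP 7.9 already uses for the distribution curves, more than 20 patients per arm at the visit.

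The cost is one extra parameter per additional modelled visit, somewhat wider CIs and some added convergence risk. No new data are needed. A baseline-by-visit term is optional and is not needed to remove the parallel-curve constraint.
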